8.2.1.5. Aim 4 Inclusion Criteria

- Born in 2005 or earlier (as age 18 or older in 2023, owing to the data providing year but not month or day of birth).
- At least one year of pharmacy and medical enrollment in HealthVerity prior to index date. A gap of up to 30 days will be allowed.
- Immunocompromised at the time of study index, using all-available lookback data (immunocompromised definition as per Infectious Disease Society of America Clinical Practice Guideline for Vaccination of the Immunocompromised Host)^{22,23}
- Have been a State of California/Louisiana resident for at least one year prior to index date

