Inclusion criteria in trials generally reflected age-related eligibility for vaccination.	For brevity, we will not discuss each of the 5 aim's different inclusion criteria here. Throughout, we used age at time vaccine was authorized or approved by FDA for time-varying exposures, age at vaccination for time-fixed exposures to reflect age-related eligibility.			
	We require continuous pharmacy and medical enrollment in HealthVerity prior to index date (FDA EUA date per vaccine) for follow-up. This is in order to establish pre-existing health status, which would have been queried at study entry in the clinical trials.			
	We require continuous California/Louisiana residency to maximize pre-index capture of vaccines, as people living outside of California /Louisiana would not have prior vaccines well captured in the registry.			
	Throughout, we will exclude people who are currently pregnant, using a validated			

- Exclusion criteria
 - Pregnant
 - Treatment with immunosuppressive therapy or diagnosis with an immunocompromising condition
 - History of COVID-19

gestational age algorithm with up to 9 months lookback. 18

Except in aim 4, where the analyses are specific to immunocompromised persons, we will exclude immunocompromised people considering claims for medications dispensed as well as and diagnosis codes.

We will exclude persons with a diagnosis of COVID-19 in any setting ≤ 90 days prior to index. We are limiting to 90 days as reinfections have become more common over the pandemic and were rare during the Fall 2020 clinical trial period. We believe 90 days represents a reasonable period in which persons then can be considered to be at risk for reinfection, and also are eligible for vaccination. ¹⁹

We will exclude individuals with discrepancies in sex and/or year of birth between HealthVerity claims and California/Louisiana immunization registry datasets, as these are key confounders in all analyses. Secondary deidentified data makes it impossible to reconcile differences, which would be expected to be resolved with primary data collection.

Treatment strategies

Receive 1 dose of a BNT162b2 adapted formulation vs. no BNT162b2 formulation or other COVID-19 vaccine (XBB.1.5 or BA.4/5 depending on timing)

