8.2.2.5. Aim 4 Exclusion Criteria

- Currently pregnant (using a validated gestational age algorithm with up to 9 months lookback) at the time of study index (code list to be listed in the appendix)
- Individuals with discrepancies in sex and/or year of birth between HealthVerity claims and California/Louisiana immunization registry datasets.
- Persons with a diagnosis of COVID-19 in any setting ≤90 days prior to index (FDA EUA date per vaccine)
- Receipt COVID-19 vaccine ≤ 90 days prior to index (FDA EUA date per vaccine)

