8.7. Data Analysis

Detailed methodology for summary and statistical analyses of data collected in this study will be documented in a statistical analysis plan (SAP), which will be dated, filed, and maintained by the sponsor. The SAP may modify the plans outlined in the protocol; any major modifications of primary endpoint definitions or their analyses would be reflected in a protocol amendment.

[figure not shown]
Throughout, we will use missing data indicator variables for absence of values in categorical variables (such as insurance payor) and exclude persons with missing data in continuous variables (age). Using indicator variables rather than imputation allows for the missing data patterns to be mathematically informative. Variables with data delivered of strings as 'Missing' or 'Unknown' values will be reported and analyzed as separate categories and included in the totals.

All steps will be completed using SAS version 9.4 and/or R.

8.7.1. Aim 1

To evaluate the VE of BNT162b2 formulations in non-pregnant, non-immunocompromised adults against medically attended COVID-19, mortality and healthcare resource utilization by age and adapted vaccine formulation.

Figure 1. Aim 1 study design

Exposure: time-varying exposure. All persons will be considered unvaccinated from FDA date of vaccine authorization/approval until, where applicable, 13 days after receipt of vaccine. In order to allow for time after dose for meaningful immunologic protection to accrue, persons will be considered vaccinated 14 days after vaccination (i.e. patients will be censored from the unvaccinated group). 20,21

For XBB.1.5 vaccine: FDA approval date 11 September 2023²

In the event that XBB uptake is low, we will instead examine BA.4/5 VE. For BA.4/5 vaccine: FDA emergency use authorization date 31 August 2022⁴

Note: this aim pertains to adults only, and therefore does not require age-specific EUA dates.

Follow-up time: From date of FDA authorization/approval until the outcome of interest, or are censored at the first of the following: 6 months of follow-up, end of medical and/or pharmacy enrollment, receipt of a non-Pfizer BioNTech vaccine or receipt of a second BNT162b2 COVID-19 vaccine dose.

Primary outcome:

A COVID-19-related encounter, regardless of setting

Secondary outcomes:

- An outpatient encounter with ICD-10-CM U07.1 "COVID-19" code

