To measure VE of BNT162b2 formulations in non-pregnant immunocompromised adults against medically attended COVID-19, mortality and healthcare resource utilization by age and adapted vaccine formulation.

Figure 3. Aim 4 study design

Note: for this aim, the inclusion criteria will additionally restrict the population to immunocompromised adults.

Exposure: time-varying exposure. All persons will be considered unvaccinated from FDA date of vaccine authorization/approval until, where applicable, 13 days after receipt of vaccine. In order to allow for time after dose for meaningful immunologic protection to accrue, persons will be considered vaccinated 14 days after vaccination.

For BA.4/5 vaccine: FDA emergency use authorization date 31 August 2022

For XBB.1.5 vaccine: FDA approval date 11 September 2023

Note: this aim pertains to adults only, and therefore does not require age-specific EUA dates.

Follow-up time: From date of FDA authorization/approval until the outcome of interest, or are censored at the first of the following: 6 months of follow-up, end of medical and/or pharmacy enrollment, receipt of a non-Pfizer BioNTech vaccine or receipt of a second BNT162b2 COVID-19 vaccine dose.

Primary outcome:

A COVID-19-related encounter, regardless of setting (primary outcome)

Secondary outcomes:

- An outpatient encounter with ICD-10-CM U07.1 "COVID-19" code
- An inpatient encounter with ICD-10-CM U07.1 "COVID-19" listed in any diagnosis position. As a sensitivity analysis, we will restrict to U07.1 in primary diagnosis field.
- An emergency department encounter with ICD-10-CM U07.1 "COVID-19" code

- COVID-19 critical illness, defined as intensive care unit [ICU] admission, mechanical ventilation, or inpatient death. If sample size allows, we will evaluate VE against each component separately in order to support V&E models.
- Negative control outcomes such as accidental injury, ingrown toenail or atopic dermatitis

Exploratory outcomes:

- An urgent care encounter with ICD-10-CM U07.1 "COVID-19" code
- All-cause mortality within 3-months of COVID-19 encounter, regardless of setting
- All-cause mortality within 3-months of COVID-19 outpatient encounter
- All-cause mortality within 3-months of COVID-19 inpatient encounter
- All-cause mortality within 3-months of COVID-19 emergency department encounter
- All-cause mortality within 3-months of COVID-19 critical illness
- All-cause mortality within 3-months of COVID-19 urgent care encounter

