5.2.1.1. Aim 3B Adult Inclusion Criteria

- 1. Born in 2004 or earlier (as age 18 or older as of the index date, owing to the data providing year but not month or day of birth).
- 2. Has COVID-19 diagnosis (ICD-10-CM code U07.1) in any setting, any position between 01 June 2022 and 30 November 2022 (first eligible code is the index date).
- 3. At least one year of continuous pharmacy and medical enrollment in HealthVerity prior to index date (ie, COVID-19 diagnosis). A gap of up to 30 days will be allowed.
- 4. Have been a State of California/Louisiana resident for at least one year prior to index date (ie, COVID-19 diagnosis)
- 5. Have continuous medical and prescription insurance coverage for at least 30 days after the index date (follow-up period).
 - The duration of the follow-up period will be required to be at least 1 month.
 - NOTE: since the evaluation of the long-term HCRU and cost starts from 1 month after the index date, this requirement for patients to have at least one month of follow-up is needed for this study.

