5.3. Variables

5.3.1. Exposures

The exposure of interest is the BNT162b2 XBB.1.5 mRNA vaccine. *In the event that XBB uptake is low, we will instead examine BA.4/5 vaccine effectiveness* (Section 5.5).

Information on vaccination status will continue to be collected on or after the authorization/approval date, therefore vaccination status will be considered as a time-varying exposure. Patients will be assigned as vaccinated or unvaccinated according to their vaccination status by each person-time record during the follow-up. A patient will be considered vaccinated from 14 days after their BNT162b2 vaccination date till the remainder of their follow-up.

The source of the exposure variables are the California and Louisiana vaccine registries and the HV (HealthVerity) Claims database. Clinical Vaccines Administered code (CVX), National Drug Codes (NDC) and Current Procedural Terminology® (CPT) codes used to identify the XBB.1.5 and BA.4/5 vaccinations are listed in the Protocol Annex.

XBB vaccinations will be enumerated using the following hierarchical definition:

- 1. Any person in HealthVerity claims data who has a record in the California/Louisiana Immunization Registry with a CVX code indicating having received the BNT162b2 XBB.1.5 monovalent mRNA vaccine will be considered vaccinated 14 days after registry event date.
- 2. Any person in HealthVerity claims data who has a record in the California/Louisiana Immunization Registry with an event indicating having received the BNT162b2 XBB.1.5 monovalent mRNA vaccine will be considered vaccinated 14 days after registry event date.
- 3. Any person in HealthVerity claims data who does not have a record in the California/Louisiana Immunization Registry but has a pharmacy claim with an NDC code indicating a BNT162b2 XBB.1.5 monovalent mRNA vaccine dose will be considered vaccinated 14 days after claim date.
- 4. Any person in HealthVerity claims data who does not have a record in the California/Louisiana Immunization Registry and does not have a pharmacy claim with an NDC code indicating a BNT162b2 XBB.1.5 monovalent mRNA vaccine dose but has a medical claim with a CPT code indicating a BNT162b2 XBB.1.5 monovalent mRNA vaccine dose will be considered vaccinated 14 days after claim date.

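### Aim 4 applies the 2023 birth-year cut to the 31 August 2022 BA.4/5 index, so everyone admitted from the 2005 birth year is 16 or 17 in an adult cohort

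*Protocol*

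**What the plan says.** - **Population.** The study information table at the front of the protocol gives the Aim 4 population as non-pregnant immunocompromised adults, age 18+.
- **Birth-year rule.** Protocol 8.2.1.5 (Aim 4) requires "Born in 2005 or earlier (as age 18 or older in 2023" and explains that the data hold only the year of birth. The rule is not varied by vaccine. Protocol 8.2.1.1 and the Aim 1 SAP, 5.2.1, carry the same rule.
- **Index date.** Protocol 8.2.2.5 (Aim 4) ties exclusions to an index that depends on the vaccine: "Persons with a diagnosis of COVID-19 in any setting ≤90 days prior to index (FDA EUA date per vaccine". Protocol 8.7.5 (Aim 4, Exposure) lists two indexes, 11 September 2023 for XBB.1.5 and, for the earlier formulation, "For BA.4/5 vaccine: FDA emergency use authorization date 31 August 2022". It also stratifies results by BA.4/5 versus XBB.1.5 era.
- **When age is taken.** Protocol Table 2 states that "we used age at time vaccine was authorized or approved by FDA for time-varying exposures". Table 5 assesses age at index and gives Aims 1 and 4 the levels 18-49, 50-64 and 65+.
- **Aim 1.** The Aim 1 SAP, 5.3.1, keeps a fallback: "In the event that XBB uptake is low, we will instead examine BA.4/5 vaccine effectiveness". Its section 5.7.3 takes the index from Table 5.1, which lists both dates.
- **Aim 3B.** Protocol 8.2.1.4.1 used 2005 although the index window was June to November 2022. The Aim 3B SAP, 5.2.1.1, uses "Born in 2004 or earlier (as age 18 or older as of the index date".

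**The concern.** The birth-year rule is justified by age in 2023, but one of the two Aim 4 indexes falls in 2022. Applied as written, the rule brings a complete birth year of minors into a cohort described as adult.

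That differs from the ordinary imprecision of year-only birth data. Imprecision misclassifies part of one birth year. A reference year that is one too late misclassifies all of it. The protocol's own text then disagrees about who is eligible and how these people enter the age adjustment, and two programmers could build different cohorts from it.

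**Working it through.** **Inputs.** Birth-year cut 2005 (Protocol 8.2.1.5); indexes 31 August 2022 and 11 September 2023 (Protocol 8.7.5); age bands (Protocol Table 5); 12 million continuously enrolled Californians, 25% pediatric and 75% adult (Protocol 8.5); 95% of adults assumed non-immunocompromised (Aim 1 SAP, 5.5).

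**1. The plan's own figure.** Age by year difference = index year − birth year. At the 2023 index, 2023 − 2005 = 18. The stated justification reproduces for that index.

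**2. The same rule at the 2022 index.** 2022 − 2005 = 17, so the cut no longer delivers age 18. Solving 2022 − birth year = 18 gives 2004.

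**3. Exact ages, counting birth dates.**

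| Index | Birth year | Age at index (birth dates) |
|---|---|---|
| 11 Sep 2023 | 2005 | 18: 254/365 (70%); 17: 111/365 (30%) |
| 31 Aug 2022 | 2005 | 17: 243/365 (67%); 16: 122/365 (33%); 18: none |
| 31 Aug 2022 | 2004 | 18: 244/366 (67%); 17: 122/366 (33%) |

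At the 2023 index the 2005 cut leaves the usual residue of about 30% of one birth year. At the 2022 index it admits a birth year in which nobody is 18. A 2004 cut brings the 2022 index back to a similar residue, about one third.

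**4. Share of the youngest band.** Ages 18-49 by year difference in 2022 are births 1973 to 2004, which is 32 birth years. Adding 2005 makes 33, and 1/33 = 3.0%.

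**5. Share of the adult cohort (assumption).** The documents give no counts by birth year. Spreading the pediatric base evenly, 0.25 × 12,000,000 / 18 ≈ 167,000 per birth year. Against 0.75 × 12,000,000 = 9,000,000 adults this is 1.9%. If the birth year is 0.5 to 1.5 times the average, the range is 0.9% to 2.8%. With the implied 5% immunocompromised share at every age, Aim 4 would have about 8,300 of 450,000 in California. If that share is lower in adolescents than in adults, the fraction is smaller.

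**6. Rough effect on the estimate (illustration).** The Aim 1 SAP, 5.5, anticipates VE between 20% and 40%. If the 2005 birth year sat at one end and everyone else in the youngest band at the other, and weight followed the 3% share, the band estimate would move by about 0.03 × (40 − 20) = 0.6 percentage points.

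**7. Age band.** Two derivations are possible, with different results:
- Index year minus birth year gives 17, and none of the three levels applies.
- 2023 minus birth year gives 18, so these people go into 18-49. One birth year is then moved at each cut-point: births in 1973 count as 50 instead of 49, and births in 1958 as 65 instead of 64.

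Only one of these can happen in a given analysis.

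**The case against.** The strongest reply is that little depends on this. Aim 4 is exploratory, its own SAP is not among the documents, and Protocol 8.7 allows a SAP to modify the protocol. Aim 3B shows that route in use, since the 2005 rule in the protocol became 2004 in the SAP. The 31 August 2022 authorization covered age 12 and older (Protocol Table 1), so the index date is right for 16- and 17-year-olds and they gain no spurious unvaccinated time before eligibility. The proposed cut also leaves some 17-year-olds in. All of this stands and limits the size of the point. It does not make the protocol text consistent, and the one VE SAP for adults that is available (Aim 1) kept the 2005 rule.

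A reader might infer more than the documents support:
- **That these people certainly have no age band, and also that the 50 and 65 cut-points shift.** These are alternatives. The 2023-minus-birth-year formula appears only in the Aim 2 SAP, Table 5.3, where the index is in 2023 and the formula is correct. Nothing applies it to a 2022 adult index. Protocol Table 5 and the Aim 1 SAP say only that age is assessed at index.
- **That Aim 1 is affected to the same degree.** Its BA.4/5 analysis is a fallback ("In the event that XBB uptake is low, we will instead examine BA.4/5 VE"). Protocol 8.7.1 also lists a BA.4/5 versus XBB.1.5 era stratification, but the Aim 1 SAP does not carry it forward.
- **That the pediatric analysis loses 1 of 6 birth years (2005 out of 2005-2010) from ages 12-17.** This would follow from the Aim 2 rule, born in 2006 or later, at the 31 August 2022 index. The Aim 2 SAP, 5.3.1 and 5.7.3, now names only XBB.1.5 as exposure and index, so the loss arises only if a pediatric BA.4/5 analysis is run.
- **That the sponsor acknowledged an error in Aim 3B.** The SAP shows a different cut, but no text says why it changed.

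**Conclusion.** The point holds for Aim 4 as written, and for Aim 1 only if a BA.4/5 analysis is run. At the 31 August 2022 index, the stated rule admits a birth year in which nobody has reached 18. This contradicts the age 18+ objective, Table 2 and the bands in Table 5.

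The consequence is minor: 1 of 33 birth years in the youngest band, and roughly 1-3% of the adult cohort. The second figure assumes birth years of similar size. For Aim 4 it also assumes an immunocompromised share that does not vary with age. The documents do not support a claim of material bias in VE. What is at issue is a mismatch between the stated population and the eligibility rule, which should be removed before the cohort is programmed.

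**What to change.** - In Protocol 8.2.1.5, or in the Aim 4 SAP, make the cut depend on the index: born in 2004 or earlier for 31 August 2022, and 2005 or earlier for 11 September 2023.
- Add the same condition to Protocol 8.2.1.1 and the Aim 1 SAP, 5.2.1, to apply if BA.4/5 is analysed.
- State that age is index year minus birth year, so that eligibility and the age bands use one derivation.
- If a pediatric BA.4/5 analysis is run, mirror the change in Aim 2: born in 2005 or later for the 2022 indexes.
- Note in the limitations that year-only birth data still leave some 17-year-olds among adults: about one third of the 2004 birth year at the 2022 index and about 30% of the 2005 birth year at the 2023 index.

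The cost is a line of text in each place and the loss of one birth year, about 3% of the birth years in the youngest band, from BA.4/5 analyses. XBB.1.5 analyses do not change.

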- A key assumption of the TND is that exposure (here, COVID-19 vaccination) does not impact the probability of selection in the case (a positive test result on a COVID-19 test) or control population (a negative test result on a COVID-19 test). It is possible that vaccinated persons may be less likely to be seek testing in order to become a case than unvaccinated persons. This, if present, would create collider stratification bias via the requirement for testing in a TND, which biases estimates away from the null and may lead to overestimations of VE. 12-14
- Owing to the case-control nature of the design, TND allows for estimation of odds ratios (OR) but not hazard or risk ratios. OR are not directly interpretable as percentage reduction in risk, which is an easily interpretable summary measure of VE. OR with a protective direction of effect (ratio < 1) will underestimate risk, leading to underestimations of VE. 15 A cohort design allows for absolute estimates of risk such as risk differences.

The use of a retrospective cohort study allows for the adoption of design principles of randomized control trials to help mitigate some of these biases.

Cohort identification will begin from the date of EUA or FDA approval for the BNT162b2 formulation. Study follow-up will occur from FDA EUA or approval date until COVID-19 diagnosis or other outcome of interest (hospitalization, emergency department visit, outpatient encounter, end of medical and/or pharmacy enrollment, or death [according to the mortality database]).

In aims 1, 2 and 4, vaccination status will be measured as a time-varying exposure. In aims 3 and 5, vaccination status will be measured as a time-fixed exposure. Exposed person-time begins 14 days after receipt of a BNT162b2 formulation. Unexposed person-time is unvaccinated person-time, as well as 0-13 days after vaccination. The unexposed group will be further stratified by previous vaccination status for relative VE: XBB.1.5 unvaccinated and BA.4/5 vaccinated; XBB.1.5 and BA.4/5 unvaccinated and at least 2 doses of mRNA vaccine (regardless of formulation), never COVID-19 vaccinated.

The full data available, from 01 December 2018, will be used as the look-back period to define patient's characteristics, clinical history, risk factors, and healthcare utilization.

TABLE 2. TARGET TRIAL AND TARGET TRIAL EMULATION

Target Trial Specification ^{16,17}	Target Trial Emulation			
Eligibility criteria				

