5.2.2. Exclusion Criteria

Patients meeting any of the following criteria will be excluded from the study analyses:

- Currently pregnant (identified with medical codes during the up to 9 months lookback prior to the index date) or immunocompromised (see algorithm below) at the time of study index
 - Immunocompromised at the time of study index defined as one inpatient and/or 2 outpatient claims 7 days apart for any of:
 - ICD-10-CM codes for HIV/AIDS using all-available lookback
 - ICD-10-CM codes for hematologic malignancy in prior year
 - ICD-10-CM codes for solid organ or bone marrow transplant in prior two years
 - NDC, HCPCS and/or ICD-10-PCS codes for immunosuppressive medication in 210 prior days. Note: 210 days was chosen to add a 30-day grace period to 180 days, given some of the most immunosuppressive medications like rituximab and ocrelizumab are given semi-annually and we wanted to minimize misclassifications due to an overly strict definition.
- 2. Individuals with discrepancies in sex and/or year of birth between HealthVerity claims and California/Louisiana immunization registry datasets.
- 3. Individuals with a diagnosis of COVID-19 in any setting ≤90 days prior to index.
- 4. Individuals who were vaccinated within 13 days prior to the index date.

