5.2.2. Exclusion Criteria

- 1. Currently pregnant (using 9 months lookback with a codelist for current pregnancy)¹ or immunocompromised (using 1 year lookback) at the time of study index (definitions are provided in the Protocol Annex)
- 2. Individuals with discrepancies in sex and/or year of birth between HealthVerity claims and California/Louisiana immunization registry datasets. In cases where sex or year of birth is unknown in either the claims or dataset but available in the other, individuals will be included and the information from the dataset where year of birth or sex is available will be used, regardless of whether the information stemmed for claims or registry data.
- 3. Persons with a diagnosis of COVID-19 (ICD-10-CM U07.1) in any setting \leq 90 days prior to index (FDA approval/EUA date per vaccine)
- 4. Receipt of COVID-19 vaccine \leq 60 days prior to index (FDA approval/EUA date per vaccine).

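### Protocol Aim 4 sets no recency limit on the claims that make a person immunocompromised at index, and its lookback no longer matches the Aim 1 SAP exclusion

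*Protocol*

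**What the plan says.** **Aim 4, Protocol.** Section 8.2.1.5 includes people "Immunocompromised at the time of study index, using all-available lookback data", with an "immunocompromised definition as per Infectious Disease Society of America Clinical Practice Guideline for Vaccination of the Immunocompromised Host". It gives no recency limit and no minimum number of claims. Section 8 states that "The full data available, from 01 December 2018, will be used as the look-back period". The Aim 4 methods in section 8.7.5 fix the two index dates: "For BA.4/5 vaccine: FDA emergency use authorization date 31 August 2022" and "For XBB.1.5 vaccine: FDA approval date 11 September 2023". Section 8.2.1.5 requires only one year of prior enrollment.

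**The other aims, Protocol.** Sections 8.2.2.1 (Aim 1) and 8.2.2.4 (Aim 3B) exclude immunocompromised people with the same all-available lookback. Table 2 says that this exclusion is made "considering claims for medications dispensed as well as and diagnosis codes".

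**The later SAPs.** The Aim 1 SAP (section 5.2.2) excludes people who are "immunocompromised (using 1 year lookback) at the time of study index", with no distinction by condition. The Aim 3B SAP (section 5.2.2) sets windows by condition: all available data for HIV/AIDS, one year for hematologic malignancy, two years for transplant, and, for drugs, "NDC, HCPCS and/or ICD-10-PCS codes for immunosuppressive medication in 210 prior days". It explains the 210 days as 180 days plus a 30-day grace period, and it requires one inpatient and/or two outpatient claims. No Aim 4 SAP is among the documents. Protocol 8.7 allows a SAP to modify the Protocol.

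**The concern.** Aim 4 is meant to describe VE in adults whose immune status is impaired at index. A lookback without a limit answers a different question for part of the cohort: whether a person was ever recorded as immunocompromised while visible in the data. For HIV or a primary immunodeficiency the two questions largely coincide. For a drug course that ended years ago, or a treated condition, they need not.

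Two things are at stake. First, people with only remote, time-limited exposure may respond to vaccination much as immunocompetent people do. If so, they move the Aim 4 estimate toward the immunocompetent value and overstate protection in the group that the aim exists to describe. Second, the Aim 1 and Aim 4 cohorts were complementary in the Protocol. Once the Aim 1 SAP shortened its window, they stay complementary only if Aim 4 changes too.

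Classification also depends on enrollment length. Two people with the same remote history can be classified differently because one has one year of visible data and the other nearly five.

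**Working it through.** **1. The plan's own figure.** The only stated number that depends on immunocompromised status is the Aim 1 SAP sample size (section 5.5): 0.75 × 12,000,000 × 0.95 = 8,550,000, which matches Table 5.4. The remaining 5% of 9,000,000 is 450,000 adults in California. This is a planning share, not a stated Aim 4 sample size.

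**2. Maximum age of a qualifying claim.** Data start on 1 December 2018.

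| Index | Days | Months (days ÷ 30.4375) |
|---|---|---|
| XBB.1.5, 11 September 2023 | 1,745 | 57.3 |
| BA.4/5, 31 August 2022 | 1,369 | 45.0 |

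These maxima apply to people enrolled throughout. The minimum is about 12 months. The XBB.1.5 maximum is 1,745 ÷ 210 = 8.3 times the drug window in the Aim 3B SAP.

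**3. Overlap with Aim 1 at the XBB.1.5 index, given one code list.**

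- Protocol Aim 4 against Protocol Aim 1: same window, so 0 days of overlap.
- Protocol Aim 4 against the Aim 1 SAP: 1,745 − 365 = 1,380 days, or 79% of the maximum window. A person whose only qualifying claim falls there would meet both definitions.

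**4. Illustration of dilution in Aim 4.** Let f be the share that qualifies only on remote claims. With equal baseline incidence and equal uptake in the two parts of the cohort,

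VE = 1 − [(1 − f)(1 − VE_current) + f(1 − VE_recovered)].

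Take VE_recovered = 40%, the top of the 20–40% planning range in the Aim 1 SAP. The values of f and VE_current are assumptions.

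| f | VE_current 20% | VE_current 10% |
|---|---|---|
| 10% | 22% | 13% |
| 25% | 25% | 17.5% |
| 50% | 30% | 25% |

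For example, with f = 50% and VE_current = 20%: 1 − (0.5 × 0.8 + 0.5 × 0.6) = 30%. If the remote-only group had half the baseline incidence, the 20% column would read 21.1% at f = 10% and 26.7% at f = 50%, so the shift shrinks but does not vanish.

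**5. Illustration of the effect on Aim 1.** If 10% to 50% of the 450,000 were remote-only, that is 45,000 to 225,000 people, or 0.53% to 2.6% of 8,550,000. On the adverse assumption that their VE is 20% and everyone else's is 40%, Aim 1 VE falls by 20 points × 0.0053 to 20 points × 0.026, to 39.9% to 39.5%.

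**6. What alignment does and does not do.** One definition in both aims makes the overlap zero by construction. It does not remove dilution if the common window is still unlimited.

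**The case against.** The strongest reply is that the governing Aim 4 rules have not been seen. The Aim 4 SAP is not supplied, the SAPs that are supplied for Aims 1 and 3B both shortened the Protocol window, and the Aim 4 SAP may do the same. That stands, and it makes the overlap conditional. A reader might infer that people already sit in both VE cohorts. The documents do not support this: within the Protocol, Aims 1 and 4 share one lookback, and the mismatch arises only if the Protocol's Aim 4 text is kept against the Aim 1 SAP.

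A reader might also infer that a single dispensing in early 2019 is enough for entry. That is not stated. Aim 4 relies on a guideline definition whose code list is not in the supplied text, and a claim-count or recency rule there cannot be ruled out. The Table 2 sentence on medication claims begins by setting Aim 4 aside and describes the exclusion in the other aims, so drug-based entry to Aim 4 is an inference from it.

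A long lookback is not wrong in itself; the Aim 3B SAP keeps it for HIV. Aim 4 is exploratory and descriptive, no formal Aim 1 versus Aim 4 comparison is planned, and results will be stratified by level of immunosuppression. That stratifier is undefined, however, so it cannot be relied on to separate people with remote claims.

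Finally, copying the Aim 3B algorithm into Aim 4 would be unsound. It was written as an exclusion for a cost aim, names only four categories, omits primary immunodeficiencies and drops people whose only transplant claims are over two years old. That would change the target population.

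**Conclusion.** The point holds in a limited form. As written, Protocol 8.2.1.5 ties status to the index date but accepts claims up to 57 months old (XBB.1.5) or 45 months old (BA.4/5), while the sponsor's later SAPs replaced the same wording with shorter windows in two other aims. The gap matters for time-limited drugs and treated conditions, not for lasting ones.

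The likely direction is toward the immunocompetent VE, if recovered people respond as immunocompetent people do. The size is unknown. The 22% to 30% range rests on assumed VE values, an assumed remote-only share, and equal incidence and uptake. The share can be counted from the data. The effect on Aim 1 is small on the same kind of assumption: 40% becomes about 39.5% to 39.9%. Overlap of the two cohorts is a possibility that the Aim 4 SAP must close, not an established fact.

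**What to change.** In the Aim 4 SAP or a Protocol amendment:

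- Keep the guideline categories of section 8.2.1.5, but set the lookback by condition type: 210 days for immunosuppressive medication and one year for hematologic malignancy, as in the Aim 3B SAP, and all available data for lasting conditions such as HIV and primary immunodeficiency. Justify the transplant window explicitly.
- State whether a minimum claim count applies, and define level of immunosuppression.
- Use the same definition and code list for the exclusion in Aim 1 SAP 5.2.2, so that the two adult VE cohorts are complementary. Reconcile that section with Aim 1 SAP 5.1, which says that the full data from December 2018 serve as the lookback.
- Report how many people qualify for Aim 4 only on older claims, and keep all-available lookback as an Aim 4 sensitivity analysis.

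No change to Aims 2, 3A or 5 is needed on this ground, since no harm from their broader exclusion has been shown.

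The cost is a somewhat smaller Aim 4 cohort with wider intervals, and a rerun of the Aim 1 exclusion if it has already been applied. The drug and malignancy windows are already written.
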